 - Renal function indicators: BUN, Serum creatinine, creatinine clearance, or eGFR
 - Electrolytes: sodium, potassium, chloride, total calcium and bicarbonate
 - Other: Creatine phosphokinase (CPK), C-reactive protein (CRP), serum ferritin, d-dimer
- [9] Coagulation: Prothrombin time (PT) and International Normalized Ratio (INR)
- [10] ONLY performed on women of childbearing potential.
- [11] Urine samples will be tested for color, appearance, specific gravity, pH, protein, glucose, occult blood, ketones, leukocyte esterase, nitrite, bilirubin, urobilinogen, and microscopic examination of urine sediment.
- [12] Swabs will be used for RT-PCR and quantitative virologic testing:
 - Positive RT-PCR collected within 7 days before Day 1 is required at screening for patient eligibility evaluation.
 - Nasopharyngeal swab for RT-PCR and viral load assessment should be collected at Day 1, 8, 14 and 28 visits. Samples are to be stored at -70°C and shipped to the Fulgent lab twice a month.
- [13] **Randomization:** Patient number and treatment arm allocation can be performed on Day 1
- [14] For recovered patients Follow-up visits may be performed via phone or telehealth, as appropriate

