9.3. SAMPLE SIZE DETERMINATION AND RATIONALE

A total of approximately 20 subjects will be randomized 1:1 in this study. The sample size is based on clinical judgment. No statistical power calculation is used to establish the sample size for this proof-of-concept study.

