### 1.4 Analysis Method

#### 1.4.1 Inferential Statistics

According to the protocol, no inferential statistics was planned. In the SAP, the inferential testing will be done as appropriate for treatment comparison.

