### 1.4.4 Method for Categorical Data

Categorical data will be analyzed by using the Fisher's exact test or Chi-square test as

appropriate. Ordinal data will be analyzed by using Mantel-Haenszel chi-square test on given scores.

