#### 3.2 Analysis of Categorical Data

C/F noted in the mock-up table, Chi-Square test is applied when no cell have expected count  $< 1$  and  $<= 20\%$  of the cells are with expected count  $< 5$ , otherwise Fisher's exact test will be applied.

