### 14.3.6 Laboratory Examination – Urinalysis

- 14.3.6.1 Urinalysis – <Item 1 and Unit>
- 14.3.6.2 Urinalysis – <Item 2 and Unit>
- 14.3.6.3 .... Refer to [Instructions and Abbreviations] of section 16 for the test terms

*<LB Layout 1: For Continuous Laboratory Test; Clinical relevance analyses will be excluded if not applicable>*

Population: Safety Population

Characteristics	Treatment Group	Difference	p-value
. Repeat Visit: No ‘Visit 1 (Screening)’ for IL-6: Visit 1 (Screening), Baseline, Adjusted Visit 3 (Day 4), Adjusted Visit 4 (Day 8), Adjusted Visit 5 (Day 11), Adjusted Visit 6 (Day 14, EOT), Visit 7 (Day 28, F1), Visit 8 (Day 45, F2)			
N (Missing)	XXX (XXX)		
Mean (SD)	XXX (XXX)		
Median (IQR)	XXX (XXX)		
Q1~Q3	XXX~XXX		
Min~Max	XXX~XXX		
		T/W <Baseline Only>	
		0.XXXX	

For W, normality is not applied <Baseline Only>

Groups Diff	§C - §S
Median (Asymptotic SE)	XXX
95% CI (HL)	XXX~XXX

Characteristics	Treatment Group	Difference	p-value
For T, normality is applied <Baseline Only>			
Groups Diff		§C - §S	
Mean (SD)		XXX (XXX)	
95% CI		XXX~XXX	
N (Missing)	XXX (XXX)		
Normal	XXX (XX.X%)		
NCS	XXX (XX.X%)		
CS (Medical History)	XXX (XX.X%)		
CS (Adverse Event)	XXX (XX.X%)		
. Repeat [Visit – Baseline] excluding Visit 1 (Screening) and Baseline			ANCOVA/W
N (Missing)	XXX (XXX)		0.XXXX
Mean (SD)	XXX (XXX)		
Median (IQR)	XXX (XXX)		
Q1~Q3	XXX~XXX		
Min~Max	XXX~XXX		
95% CI (WI)	XXX~XXXwt		
For W, normality is not applied			
Groups Diff		§C - §S	
95% CI (HL)		XXX~XXX	
For ANOVA, normality is applied	XXX (XXX)		
LsMean (SE)	XXX~XXX		
95% CI of LsMean			
Groups Diff. (T)		§C-§S	
Difference of LsMean		XXX	
95% CI of LsMean		XXX~XXX	
ANCOVA Model (p-value 0.XXXX) with effect Treatment (p-value 0.XXXX), Baseline (p-value 0.XXXX), Treatment*Baseline (p-value 0.XXXX).			
. Repeat [<Baseline> to <Visit>]			
N (Missing)	XXX (XXX)		
Relieved	XXX (XX.X%)		
Unchanged	XXX (XX.X%)		
Worsened (Medical History)	XXX (XX.X%)		
Worsened (Adverse Event)	XXX (XX.X%)		

For Item excluding IL-6 Baseline is Visit 2 (Day 1) data, or is Visit 1 if Visit 2 (Day 1) is null

For IL-6 Baseline is Visit 2 (Day 1) data

Refer to [Instructions and Abbreviations] of title pages for Transition of Clinical Relevance

**<LB Layout 2: For Categorical Urinalysis Test, including pH;  
 MHCHISQ for PH, C/F for else>**

Population: Safety Population

Characteristics	Treatment Group	p-value

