. Repeat Visit: Visit 1 (Screening), Baseline, Adjusted Visit 3 (Day 4), Adjusted Visit 4 (Day 8), Adjusted Visit 5 (Day 11), Adjusted Visit 6 (Day 14, EOT), Visit 7 (Day 28, F1), Visit 8 (Day 45, F2)		MHCHISQ / C/F <Baseline Only> 0.XXXX
N (Missing)	XXX (XXX)	
<Value 1>	XXX (XX.X%)	
<Value 2>	XXX (XX.X%)	
<Value 3>	XXX (XX.X%)	
N (Missing)	XXX (XXX)	
Normal	XXX (XX.X%)	
NCS	XXX (XX.X%)	
CS (Medical History)	XXX (XX.X%)	
CS (Adverse Event)	XXX (XX.X%)	
. Repeat [<Visit> – <Baseline>] for pH Repeat [<Baseline> to <Visit>] for else For <Visit> excluding Visit 1 (Screening) and Baseline		MHCHISQ / C/F
N (Missing)	XXX (XXX)	0.XXXX
<Value 1>	XXX (XX.X%)	
<Value 2>	XXX (XX.X%)	
<Value 3>	XXX (XX.X%)	
. Repeat [<Baseline> to <Visit>]		
N (Missing)	XXX (XXX)	
Relieved	XXX (XX.X%)	
Unchanged	XXX (XX.X%)	
Worsened (Medical History)	XXX (XX.X%)	
Worsened (Adverse Event)	XXX (XX.X%)	

Baseline is Visit 2 (Day 1) data, or is Visit 1 if Visit 2 (Day 1) is null

Refer to [Instructions and Abbreviations] of title pages for Transition of Clinical Relevance

[For Color and Appearance] Data of normal values will be coded as ‘Normal’, and data not in normal values will be coded as ‘Abnormal’.

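### SAP LB Layout 2 puts a between-arm p-value on unordered baseline-to-visit pairs for every categorical urinalysis item except pH, so that p-value does not measure change

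*SAP*

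**What the plan says.** SAP 1.4.4 gives categorical data to Fisher's exact or the Chi-square test and then adds a rule for ordered data: "Ordinal data will be analyzed by using Mantel-Haenszel chi-square test on given scores". SAP 3.2 decides between the two unordered tests. "Chi-Square test is applied when no cell have expected count" below 1 and at most 20% of cells are expected to hold fewer than 5; otherwise Fisher applies.

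LB Layout 2 in SAP 14.3.6 covers categorical urinalysis, including pH, with the note "MHCHISQ for PH, C/F for else". Its change block, which carries a between-arm p-value, takes visit minus baseline for pH and then says "Repeat [<Baseline> to <Visit>] for else". Color and appearance are coded Normal/Abnormal; no other item is collapsed. A separate block counts Relieved, Unchanged and Worsened patients without a p-value.

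The items are in protocol 1.3, footnote 11. Besides color, appearance, specific gravity and pH they are "protein, glucose, occult blood, ketones, leukocyte esterase, nitrite, bilirubin, urobilinogen, and microscopic examination of urine sediment". Neither document gives their result categories.

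On size and purpose, protocol 9.3 states "A total of approximately 20 subjects will be randomized 1:1 in this study" and "No statistical power calculation is used to establish the sample size for this proof-of-concept study". Protocol 9.8.4 planned no inference. SAP 1.4.1 changes this: "In the SAP, the inferential testing will be done as appropriate for treatment comparison".

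**The concern.** A row headed as baseline to visit, with a p-value, will be read as a comparison of change. The test behind it sees only labels. A move from negative to 2+ and a move from 2+ to negative are simply two different categories. So are staying negative and staying at trace, although neither patient has changed.

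Two consequences follow:

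- If the arms happen to differ at baseline and results are stable, the change row repeats the baseline difference as if it were change, at each of the six post-baseline visits (Visits 3 to 8).
- If an item is graded, a shift in one direction on CX-4945 is spread over many pair categories, and an order-blind test on about 20 patients picks it up less often than a test of the change itself.

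**Working it through.** The plan states no power or error figure for this analysis, so there is nothing to reproduce. Inputs from the documents are about 20 patients at 1:1, taken as 10 per arm; the test assignment in LB Layout 2; and the switching rule in SAP 3.2. The SAP gives no significance level for these tests, so two-sided 5% is assumed.

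**Which test applies.** With 10 per arm, a cell's expected count is half its column total. A column total below 10 puts both of its cells below 5. Since 20 patients fill at most two columns of 10, the 20% limit is met only with exactly two categories of 10 patients each. Every other table goes to Fisher.

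**No patient changes.** The table of pairs is then the baseline table.

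- 8 negative and 2 trace v 2 negative and 8 trace, at both visits: Chi-square = 20 × (8×8 − 2×2)² / (10×10×10×10) = 20 × 3600 / 10000 = 7.2, p = 0.007. All expected counts are 5, so SAP 3.2 selects Chi-square. Fisher would give 2 × (2025 + 100 + 1) / 184756 = 0.023.
- 0/10 v 5/10 at grade 1, at both visits: Fisher p = 2 × C(10,5) / C(20,5) = 2 × 252 / 15504 = 0.033.

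Every change score is zero in both examples. Two levels are enough, so this part does not depend on grading.

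**Identical baselines, real shift (grading assumed).** Each arm starts at grades 0,0,0,0,1,1,2,2,3,3. The Mantel-Haenszel statistic on the change score is (N − 1)r², on 1 df.

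- One-grade rise in 6/10 v 0/10 (two from grade 0, two from grade 1, one each from grades 2 and 3): r² = (6×10)² / (10×10×6×14) = 0.4286; 19 × 0.4286 = 8.14, p = 0.004. Fisher on the pairs gives p = 0.295.
- One-grade rise in 5/10 v 0/10 (two from grade 0, one each from grades 1 to 3): r² = (5×10)² / (10×10×5×15) = 0.3333; 19 × 0.3333 = 6.33, p = 0.012. Fisher on the pairs gives p = 0.664.

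**Simulated power (all inputs assumed).** Four grades, 10 per arm, one-grade rise in 60% on CX-4945 v 10% on SOC, SAP 3.2 switching rule. Figures carry simulation error of a few points.

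| Baseline shares, lowest grade first | One-grade falls | Pairs | Mantel-Haenszel on change |
|---|---|---|---|
| 50/25/15/10% | 10% on SOC only | 34% | 64% |
| 50/25/15/10% | 10% in both arms | 38% | 50% |
| 80/10/7/3% | 10% in both arms | 52% | 58% |

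For a smaller effect, 30% v 10% rising with falls on SOC only, both are low: about 7–8% v 16–19%.

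A second set used five grades and equal 10% falls, with a rise in 50% v 10%. Pairs v Mantel-Haenszel gave 35% v 44% (80% starting at the lowest grade), 22% v 38% (50%) and 16% v 33% (30%).

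**Arms truly alike.** In the same five-grade set, the pairs test rejected in 0.9% to 4.4% of simulated trials.

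**The case against.** Several objections stand and limit the point.

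- **The conflict with SAP 1.4.4 is conditional.** A reader might infer that the layout plainly breaks the SAP's own rule for ordinal data. The documents do not support that. The layout is titled for categorical tests, and the result categories are not given. If items are recorded as negative/positive, 1.4.4 is not breached.
- **Error rates are not inflated.** A reader might take the no-change examples to mean that false positives exceed 5%. They do not, because randomisation preserves test size. A gap of 6 or more patients between arms of 10 has probability about 1.2% at 50% prevalence and 0.2% at 20%. The p = 0.007 needs exactly 10 patients in each category. The same table also prints a baseline between-arm p-value, so the imbalance is visible.
- **The large power gap needs favourable inputs.** The 34% v 64% figure lets patients fall a grade on SOC but not on CX-4945. Equal falls and mostly negative baselines shrink the gap to 6 points.
- **Clinically relevant worsening is shown elsewhere.** The Relieved/Unchanged/Worsened rows give direction by arm and visit. Protocol 8.3.1 makes clinically significant laboratory abnormalities adverse events, so they reach the AE tables.
- **No decision hangs on these p-values.** A reader might infer that the primary endpoint is compromised. That endpoint is adverse events, including laboratory findings, and the safety measures in protocol 9.2.1 name chemistry, hematology and coagulation but not urinalysis.

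One reply fails: that the bracketed row may mean something other than value pairs. SAP table 14.2.3.1 uses the same form with Positive to Negative and Positive to Positive rows, and nothing in Layout 2 suggests another meaning.

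**Conclusion.** The point holds, and it is minor. For every categorical urinalysis item except pH, the post-baseline p-value compares unordered baseline-to-visit pairs and so mixes baseline difference with change. This follows from the layout itself and applies to two-level items too, including color and appearance coded Normal/Abnormal. With 10 per arm it can give p = 0.007 or 0.033 when no patient has changed, although such imbalance is uncommon.

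The departure from SAP 1.4.4 and the loss of power hold only if an item is recorded in ordered grades. In the four-grade scenarios with 60% v 10% rising, the loss runs from about 30 points (34% v 64%) through 12 (38% v 50%) to 6 (52% v 58%). At 30% v 10% rising, either test would usually miss the shift, so the fix does not turn a trial of about 20 patients into a sensitive one. What it does is make the p-value answer the question that its row asks.

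**What to change.** In LB Layout 2:

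1. State the result categories of each item.
2. For any item in ordered grades, assign numeric scores, test visit grade minus baseline grade with MHCHISQ as the layout does for pH, and use MHCHISQ on the grades for the baseline comparison.
3. For two-level items (nitrite, color, appearance), apply Chi-square/Fisher to a change category of worsened, unchanged or improved, not to raw pairs.
4. Keep the baseline-to-visit pairs as a descriptive shift table without a p-value.

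The cost is SAP wording and modest programming. The Mantel-Haenszel method is already specified for pH, and no new data are needed. The small downside is that grades need numeric scores, which should be fixed before the results are seen.

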### 14.3.7 Physical Examination

#### 14.3.7.1 Physical Examination – All Abnormalities

Population: Safety Population

Characteristics	Treatment Group
. Repeat Visit:	
Visit 1 (Screening), Visit 2 (Day 1), Visit 4 (Day 8),	
Visit 6 (Day 14, EOT), Visit 7 (Day 28, F1), Visit 8 (Day 45, F2)	
N (Missing)	XXX (XXX)
At least one below	XXX (XXX.X%)
~ <Body System 1>	XXX (XXX.X%)
~ NCS	XXX (XXX.X%)
~CS (Medical History)	XXX (XXX.X%)
~CS (Adverse Event)	XXX (XXX.X%)
~ <Body System 2>	XXX (XXX.X%)
~ NCS	XXX (XXX.X%)
~CS (Medical History)	XXX (XXX.X%)
~CS (Adverse Event)	XXX (XXX.X%)
~ <Body System 3>	XXX (XXX.X%)
~ NCS	XXX (XXX.X%)
~CS (Medical History)	XXX (XXX.X%)
~CS (Adverse Event)	XXX (XXX.X%)
...	...

### 14.3.8 Vital Signs, Body Weight and SpO2

- 14.3.8.1 Vital Signs – Temperature [degree C]
- 14.3.8.2 Vital Signs – Respiratory Rate [breaths/min]
- 14.3.8.3 Vital Signs – Systolic Blood Pressure [mmHg]
- 14.3.8.4 Vital Signs – Diastolic Blood Pressure [mmHg]
- 14.3.8.5 Vital Signs – Heart Rate [beats/min]
- 14.3.8.6 Vital Signs – Weight [kg]
- 14.3.8.7 Vital Signs – Pulse Oxygen Saturation (SpO2) [%]

Population: Safety Population		Treatment Group	p-value
Characteristics			
. Repeat Visit:			
Visit 1 (Screening), Baseline,			
Adjusted Visit 3 (Day 4), Adjusted Visit 4 (Day 8), Adjusted Visit 5 (Day 11),			
Adjusted Visit 6 (Day 14, EOT), Visit 7 (Day 28, F1), Visit 8 (Day 45, F2)			
N (Missing)	XXX (XXX)		
Mean (SD)	XXX (XXX)		
Median (IQR)	XXX (XXX)		
Q1~Q3	XXX~XXX		
Min~Max	XXX~XXX		
For W, normality is not applied		§C - §S	
Groups Diff			
Median (Asymptotic SE)	XXX		
95% CI (HL)	XXX~XXX		
For T, normality is applied		§C - §S	
Groups Diff			
Mean (SD)	XXX (XXX)		
95% CI	XXX~XXX		
For Temperature, Respiratory Rate, Heart Rate, Pulse Oxygen Saturation (SpO2)			
Normal	XXX (XXX.X%)	C/F	
Abnormal	XXX (XXX.X%)	0.XXXX	
. Repeat [Visit – Baseline] excluding Visit 1 (Screening) and Baseline			ANCOVA/W
N (Missing)	XXX (XXX)		0.XXXX
Mean (SD)	XXX (XXX)		
Median (IQR)	XXX (XXX)		
Q1~Q3	XXX~XXX		
Min~Max	XXX~XXX		
95% CI (WI)	XXX~XXXwt		
For W, normality is not applied		§C - §S	
Groups Diff			
95% CI (HL)	XXX~XXX		
For ANCOVA, normality is applied		XXX (XXX)	
		XXX~XXX	
LsMean (SE)			
95% CI of LsMean			
Groups Diff. (T)	§C- §S		
Difference of LsMean	XXX		
95% CI of LsMean	XXX~XXX		

ANCOVA Model (p-value 0.XXXX) with effect Treatment (p-value 0.XXXX), Baseline (p-value 0.XXXX), Treatment\*Baseline (p-value 0.XXXX).

Baseline is Visit 2 (Day 1) data, or is Visit 1 if Visit 2 (Day 1) is null

[Temperature] Normal: <36.6°C from axillary site, or < 37.2°C from oral site or < 37.8°C from rectal or tympanic site

[Respiratory Rate] Normal: < 20 breaths/min

[Heart Rate] Normal: <90 beats/min

[Pulse Oxygen Saturation (SpO2)] Normal: ≥ 96%

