8.2.1.3. Vital Signs and Physical Examination

Patients will have a full physical examination to include an examination of all major body systems, height (at screening only), weight, blood pressure and pulse rate, which may be performed by a physician, registered nurse or other qualified health care provider, as acceptable according to local regulation. Symptom-directed physical examination should be limited to systems of primary relevance (i.e., cardiovascular, respiratory, and systems associated with symptoms). Changes from baseline abnormalities should be recorded at each subsequent physical examination. New or worsened abnormalities should be recorded as an AE.

Pulse oximetry should be collected prior to collection of the blood pressure, pulse rate, and temperature. Oxygen levels should be evaluated on the finger in accordance with the site's standard procedures. All abnormalities will be evaluated by the study physician.

Blood pressure, heart rate, respiration rate, and temperature should be recorded after approximately 5 minutes rest. An abbreviated physical exam is an assessment for emergent toxicities or changes from prior visits and a symptom directed exam conducted by a physician, trained physician's assistant or nurse practitioner, as acceptable according to local regulation.

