8.3.1. Definitions of AE

An AE is defined as any unfavorable or unintended sign, symptom, or disease that occurs or is reported by the patient to have occurred, or a worsening of a pre-existing condition. An AE may or may not be related to the study treatment.

AEs will be elicited through direct questioning and patient reports. Any abnormality in physical examination findings or laboratory results that the investigator believes is clinically significant (CS) to the research patient and that occurred after initiation of the first study treatment will be reported as AEs. Abnormal findings that are NOT clinically significant should not be recorded as an AE.

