8.3.3. Classification of AEs

8.3.3.1. Severity of AE

As study population is outpatients with moderate COVID-19, a standardized toxicity grading scale is modified to reflect the study population. Toxicity Grading Scale for Healthy Adult and Adolescent Volunteers Enrolled in Preventive Vaccine Clinical Trials will be used for grading AEs associated with systemic (general) abnormalities, vital signs, illnesses and lab abnormalities. Full guidelines may be obtained at <https://www.fda.gov/media/73679/download>.

Table 6. Toxicity Grading General Guidelines

Grade	Description
Grade 1	Mild; No interference with activity
Grade 2	Moderate; Some interference with activity not requiring medical intervention
Grade 3	Prevents daily activity and requires medical intervention
Grade 4	Potentially Life-threatening ER visit or hospitalization
Grade 5	Death related to AE.

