## (5) Efficacy Endpoints:

- **Time to COVID-19-Related Clinical Signs Normalization: Normal when all below are met**
  - (1) Fever is <36.6°C from axillary site, or < 37.2°C from oral site, or < 37.8°C from rectal or tympanic site, or <37.2°C from forehead by using non-contact infrared thermometers
  - (2) Respiratory rate is < 20 bpm while breathing room air
  - (3) SpO2 ≥ 96% in room air without shortness of breath or dyspnea caused by COVID-19
  - (4) Heart rate < 90 beats per minute

If some signs listed above were caused by other conditions documented in the medical history and started before COVID-19, the patient can be considered as recovered, when these signs return to the previous (pre-COVID-19) values
- **Oxygen Saturation Level Normalization: Normal when SpO2 ≥ 96%**
- **Resolution of moderate COVID-19-Related Symptoms when all below are met:**
  - No key COVID-19-related symptoms scored higher than 1.
  - If some symptoms were caused by other conditions documented in the medical history and started before COVID-19 (e.g, insomnia), the patient can be considered as recovered, when these symptoms return to the previous (pre-COVID-19) value.
- **SARS-CoV-2 Viral Clearance: negative RT-PCR**

- **NIAID 8-Point Clinical Progression Outcomes Scale:**
  - 1 - Death
  - 2 - Hospitalized, on invasive mechanical ventilation or extracorporeal membrane oxygenation (ECMO)
  - 3 - Hospitalized, on non-invasive ventilation or high flow oxygen devices
  - 4 - Hospitalized, requiring supplemental oxygen
  - 5 - Hospitalized, not requiring supplemental oxygen - requiring ongoing medical care (COVID-19 related or otherwise)
  - 6 - Hospitalized, not requiring supplemental oxygen - no longer requires ongoing medical care
  - 7 - Not hospitalized, limitation on activities and/or requiring home oxygen
  - 8 - Not hospitalized, no limitations on activities
- **EQ-5D-5L Imaginable Health Status Improvement: Imaginable Health Status <90 at baseline and ≥ 90 after baseline**
- **Time to Response (Normalization / Resolution / Viral Clearance / Improvement)**

Time to Response (days), Best Case Scenario  
 = Days to first response for responder,  
 = Days to last observation for non-responder (censored)

Time to Response (days), Worst Case Scenario  
 = Days to first response for responder,  
 = Days to planned last observation date (31 for EQ-5D-5L and SARS-COV-2 Viral Clearance at visit 7, 45 for others at visit 8) for non-responder (censored)

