### <TTR Figure Layout: For Response Proportion>

## 14.2.1 COVID-19-Related Clinical Signs

### 14.2.1.1 Time to COVID-19-Related Clinical Signs Normalization

*Use TTR Layout*

*Footnote: refer to table 14.3.8 for the normal status of each symptom by visit*

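### Safety table 14.3.8 counts low heart rate, respiratory rate and temperature as 'Normal' and has no category row for blood pressure (minor, inexpensive improvement)

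*SAP*

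**What the plan says.** SAP 14.3.8 is headed as a Safety-population table and has one sub-table each for temperature, respiratory rate, systolic pressure, diastolic pressure, heart rate, weight and SpO2. Each sub-table gives N, mean, SD, median, quartiles, minimum and maximum by visit, the change from baseline and a group difference.

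Normal/Abnormal counts, with a chi-square or Fisher p-value, are restricted by the row label "For Temperature, Respiratory Rate, Heart Rate, Pulse Oxygen Saturation (SpO2". Blood pressure is not in that list. The footnotes define Normal as a heart rate below 90 ("Heart Rate] Normal: <90 beats/min"), a respiratory rate below 20, a temperature below a ceiling that depends on the site of measurement, and an SpO2 of at least 96%.

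These are the recovery limits of the efficacy endpoint. SAP Instructions and Abbreviations, (5) Efficacy Endpoints, lists "Heart rate < 90 beats per minute" among the conditions for normalization of clinical signs. The footnote to 14.2.1.1 makes the link explicit: "refer to table 14.3.8 for the normal status of each symptom by visit".

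Protocol 9.2.1 names changes in temperature, pulse, respiratory rate and both blood pressures as safety measures, and safety is the primary objective. Protocol 9.8.4.3 asks that vital-sign findings be listed and/or summarized.

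**The concern.** A recovery limit and a safety range answer different questions. For recovery it is enough that heart rate has come down below 90. In a safety table, a row headed Normal is read as saying that the value was not abnormal in either direction, and a limit with no lower bound cannot support that.

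The low direction is worth counting here. Protocol 5.1.1 requires a respiratory rate of at least 20 or a heart rate of at least 90 at entry, so both can be expected to fall as patients recover. A mean change then mixes recovery with any excessive lowering. Protocol 8.2.1.6 also notes that the 5-HT3 antagonist premedication may predispose to arrhythmias.

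Vital signs are treated differently from the other safety data. The laboratory, physical-examination and ECG tables (SAP 14.3.2 to 14.3.7 and 14.3.9) have rows for abnormal findings that are or are not clinically significant. Table 14.3.8 has none. Protocol 8.3.1 says "Abnormal findings that are NOT clinically significant should not be recorded as an AE". A low vital sign judged not clinically significant is therefore counted as a patient in no planned safety table. It appears only in the distribution summaries and the listings.

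**Working it through.** The plan has no figure of its own to reproduce on this point. The check is a reading of the limits, followed by two illustrations with assumed values.

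**1. Limits side by side**

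| Sign | Recovery limit, Instructions (5) | Normal in 14.3.8 | What Abnormal counts | Where a low value goes |
|---|---|---|---|---|
| Heart rate | < 90 | < 90 | ≥ 90, high values | Normal |
| Respiratory rate | < 20 | < 20 | ≥ 20, high values | Normal |
| Temperature | below site ceiling | below site ceiling | at or above ceiling, high values | Normal |
| SpO2 | ≥ 96% | ≥ 96% | < 96%, low values | Abnormal, as it should |
| Systolic, diastolic pressure | none | no category row | nothing | not counted |

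High values are counted by visit for three signs. Low values are not counted for those three, and neither direction is counted for the two pressures.

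**2. Heart rate at one visit**

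Protocol 9.3 plans about 20 patients randomized 1:1, so take 10 per arm. Assume Arm A values of 60, 63, 66, 70, 73, 76, 79, 82, 85, 89, with the lowest k replaced by 35, and all Arm B values in 60 to 89. With the SAS default quartile (assumed) and n = 10, Q1 is the 3rd lowest value and the median is the mean of the 5th and 6th. For k/10 against 0/10 the two-sided Fisher p is 2·C(10,k)/C(20,k). For example, k = 3 gives 2 × 120/1140 = 0.211, and k = 5 gives 2 × 252/15504 = 0.033.

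| k | Normal row, A v B | Min | Q1 | Median | Mean | A low-value row would print | Fisher p |
|---|---|---|---|---|---|---|---|
| 0 | 10/10 v 10/10 | 60 | 66 | 74.5 | 74.3 | 0/10 v 0/10 | – |
| 1 | 10/10 v 10/10 | 35 | 66 | 74.5 | 71.8 | 1/10 v 0/10 | 1.00 |
| 2 | 10/10 v 10/10 | 35 | 66 | 74.5 | 69.0 | 2/10 v 0/10 | 0.474 |
| 3 | 10/10 v 10/10 | 35 | 35 | 74.5 | 65.9 | 3/10 v 0/10 | 0.211 |
| 4 | 10/10 v 10/10 | 35 | 35 | 74.5 | 62.4 | 4/10 v 0/10 | 0.087 |
| 5 | 10/10 v 10/10 | 35 | 35 | 55.5 | 58.6 | 5/10 v 0/10 | 0.033 |

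The Normal row does not react to k. The neighbouring rows do, from k = 1 onward, but they do not print the count.

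**3. Systolic pressure over the four visits on Days 4, 8, 11 and 14**

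Assume Arm A baselines for patients 1 to 10 of 104, 108, 112, 116, 120, 124, 128, 132, 138, 146 (sum 1228). Assign the same ten visit values to the patients in four ways:

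- patient 1 low: 86, 116, 104, 108, 120, 124, 128, 98, 112, 132
- patient 2 low: 104, 86, 108, 112, 124, 132, 116, 98, 120, 128
- patient 3 low: 112, 108, 86, 98, 120, 116, 128, 124, 104, 132
- patient 5 low: 98, 108, 104, 124, 86, 116, 132, 120, 112, 128

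Each has visit sum 1128, mean 112.8 and minimum 86. The mean change is (1128 − 1228)/10 = −10.0. The squared changes sum to 2544 each time, so the SD is √((2544 − 100²/10)/9) = √(1544/9) = 13.098. The change has minimum −34, Q1 −18, median −8, Q3 0 and maximum 8 in all four.

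The baselines, the visit values and the sum of squared changes are the same, so the sum of baseline × visit value is the same too. The ANCOVA, with or without the treatment-by-baseline term, uses Arm A only through these sums, so it is the same whatever Arm B shows. Shapiro-Wilk p on the change is 0.63 to 0.82, above the 0.05 rule in SAP 3.1, so the ANCOVA branch applies.

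One assignment used at all four visits means 1 patient was ever below 90. A different one at each visit means 4 patients. Every by-visit row of the table is the same in both cases. Days 28 and 45 are left out because recovered patients may be followed by phone or telehealth.

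**The case against.** The reuse of the limits is deliberate and disclosed. The cut-offs stand in footnotes beneath the table, and 14.2.1.1 needs these rows. High values are the disease-relevant direction, and they are counted. That stands, and it is why the rows should be relabelled, not removed.

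Safeguards exist outside the category rows. Protocol 8.2.1.3 says "All abnormalities will be evaluated by the study physician" and "New or worsened abnormalities should be recorded as an AE". Under Protocol 8.3.3.1 the toxicity scale "will be used for grading AEs associated with systemic (general) abnormalities, vital signs, illnesses and lab abnormalities". All collected data are listed (Protocol 9.7), and about 20 patients can be counted by hand. A heart rate of 35 would be expected to reach the adverse-event tables. This also stands. The remaining gap concerns values judged not clinically significant, and the convenience of a direct count.

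The systolic example was built so that the summaries coincide. It shows that this can happen, not that it is likely.

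A reader might infer that the table gives no number of patients with a low or high value for any of the five signs. The documents do not support that. For heart rate, respiratory rate and temperature, the Abnormal row is the number of patients with a high value, by visit and arm.

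**Conclusion.** The point holds as a minor, optional improvement. A stated rule counts low heart rate, respiratory rate and temperature as Normal in a table that serves the primary safety objective, and blood pressure has no category count in either direction. What is missing is a per-arm patient count of low values for those three signs, and of low or high values for systolic and diastolic pressure.

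A reader might go further and infer that low values are hidden or that the SAP falls short of the protocol. Neither follows. Low values remain visible in Min~Max, quartiles, change from baseline and listings, and Protocol 9.8.4.3 is satisfied by a listing or a summary. No efficacy or adverse-event result changes.

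The reading of the limits rests on the text alone. The numerical illustrations rest on assumed values, 10 patients per arm and the SAS default quartile. They are not predictions for this trial.

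**What to change.** - Relabel the existing rows 'meets / does not meet COVID-19 recovery limit' and keep the reference from 14.2.1.1.
- Add, per arm, the number of patients with any low post-baseline value for heart rate, respiratory rate and temperature, and with any low or any high post-baseline value for systolic and diastolic pressure. A patient with both a low and a high pressure counts in both rows.
- For low pressure, use systolic < 90 and diastolic < 60 mm Hg. Protocol 6.1.5 gives these in its definition of shock among the reasons for stopping CX-4945, so they serve as a pragmatic flag, not as a reference range.
- Write the remaining cut-offs into the SAP before database lock. Take them from the protocol's toxicity scale where it grades that sign and direction, and choose them explicitly otherwise. Protocol Appendix 2 only links to the scale, and the documents state no high blood-pressure limit.

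The values are already collected. The cost is SAP wording, a slightly longer table and the choice of cut-offs that the documents do not supply.
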